10.2 Secondary Endpoints

10.2.1 Itch score based on the Shiratori's severity criteria

Analysis items are shown below.

Itch score based on the Shiratori's severity criteria: Higher of daytime or night-time; daytime and night-time

The mean itch score and the change from baseline at each time point will be calculated using the same calculation formula as that for the mean NRS score and change from baseline shown in "10.1 Primary Endpoint."

10.2.1.1 Changes from the baseline in the itch score based on the Shiratori's severity criteria

The same analysis as "10.1.1.1.1 Primary analysis" will be performed. However, the baseline of each item will be used as a covariate in the model. Examination of the dose-response relationship using contrasts will not be conducted. The same analysis as "10.1.2.1 Change from baseline in the mean NRS score" will be performed.

Assessment time points: (analysis using a model) Weeks 1, 2, 3, 4, 5, 6, 7, and 8 (Others) Weeks 1, 2, 3, 4, 5, 6, 7, and 8, Follow-up Weeks 1 and 2

10.2.1.2 Itch score based on the Shiratori's severity criteria

The same analysis as "10.1.2.2 Mean NRS score" will be performed.

Assessment time points: Weeks -1, 0, 1, 2, 3, 4, 5, 6, 7, and 8, Follow-up Weeks 1 and 2

10.2.2 Skindex-16

Subscores will be the symptoms score, emotions score, and functioning score. Analysis items are shown below.

Skindex-16: Overall score, subscores (symptoms, emotions, and functioning)

10.2.2.1 Changes from baseline in Skindex-16

The same analysis as "10.1.1.1.1 Primary analysis" will be performed. However, the baseline

Protocol No. MR13A9-4 Version: 1.0

of each item will be used as a covariate in the model. Examination of the dose-response relationship using contrasts will not be conducted. The same analysis as "10.1.2.1 Change from baseline in the mean NRS score" will be performed.

Assessment time points: Weeks 4 and 8

10.2.2.2 Skindex-16

The same analysis as "10.1.2.2 Mean NRS score" will be performed.

Assessment time points: Weeks 0, 4, and 8

10.2.3 5-D Itch Scale

Analysis items are shown below.

5-D Itch Scale: Total score

10.2.3.1 Changes from baseline in 5-D itch scale

The same analysis as "10.1.1.1.1 Primary analysis" will be performed. However, baseline of the total score will be used as a covariate in the model. Examination of the dose-response relationship using contrasts will not be conducted. The same analysis as "10.1.2.1 Change from baseline in the mean NRS score" will be performed.

Assessment time points: Weeks 4 and 8

10.2.3.2 5-D Itch Scale

The same analysis as "10.1.2.2 Mean NRS score" will be performed.

Assessment time points: Weeks 0, 4, and 8

10.2.4 Patient Global Impression of Change (PGIC)

For measurements, the number and percentage of subjects will be presented. A two-sample Wilcoxon test will be used for comparisons between the placebo group and each of the MR13A9 0.25, 0.5, and $1.0\,\mu\text{g/kg}$ groups. The percentages for measurements will be presented graphically.

Assessment time points: At final assessment in the treatment period

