7.5.4.4 Randomization of subjects

Based on the treatment assignment table, the subject registration center will randomly assign subjects eligible for tertiary registration to 4 treatment groups by a dynamic allocation method using 2 stratification factors: prior treatment with nalfurafine hydrochloride (for \geq 2 consecutive weeks in the year prior to the informed consent procedure) and specific signs or symptoms during the screening period (Appendix 2) confirmed before dialysis at Week 0.

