7.6.2 Rationale for the sample size

In the non-Japanese phase II clinical study (CR845-CLIN2101), the change from baseline in NRS score at Week 8 (mean \pm standard deviation) was -3.9 ± 2.48 , -2.8 ± 2.24 , and -3.4 ± 2.34 in the MR13A9 0.5 μ g/kg, 1.0 μ g/kg, and combined (CR845 all doses) groups, respectively, versus -1.9 ± 2.29 in the placebo group. The difference in the change from

baseline in NRS score (least squares mean \pm standard error) in each of the MR13A9 0.5 μ g/kg, 1.0 μ g/kg, and combined groups versus the placebo group was -1.8 ± 0.50 , -0.8 ± 0.52 , and -1.3 ± 0.41 , respectively.

For the present study, the MR13A9 0.5 and 1.0 μ g/kg groups were assumed to have a similar change in NRS score at Week 8 of the treatment period to that observed in the MR13A9 combined group in the non-Japanese phase II clinical study. The MR13A9 0.25 μ g/kg group, for which no efficacy results were obtained, was assumed to have about half the change in NRS score assumed above. The mean difference in NRS score between each of the MR13A9 0.25, 0.5, and 1.0 μ g/kg groups and the placebo group was assumed to be -0.6, -1.3, and -1.3, respectively, with a common standard deviation of 2.5. When the dose-response relationship for the MR13A9 0.25, 0.5, and 1.0 μ g/kg groups was evaluated using the contrast patterns shown in "13.5.2.1.1 Primary analysis," with a two-sided significance level of 5% and a sample size of 60 subjects per group, a contrast pattern of 3, 1, -2, -2 (placebo, 0.25, 0.5, 1.0 μ g/kg) produced a statistical power of 91.7%. Statistical power is more than 80% when the MR13A9 0.5 or 1.0 μ g/kg group (60 subjects per groups) was compared with the placebo group.

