All statistical tests will be performed using a two-sided significance level of 5%; however, a two-sided significance level of 15% will be used for the analysis of between-group imbalance. Summary statistics will be presented as the number of subjects, mean, standard deviation, minimum, median, maximum, and quartile. Unless otherwise specified, data will be tabulated by group and by time point. Week 0 will be the baseline.

SAS System Release 9.4 for Windows (SAS Institute Inc.) will be used to conduct the analysis.

4. Analysis Sets

The analysis sets are defined as follows. When the full analysis set (FAS) and the per protocol set (PPS) are used as analysis sets, analyses will be performed based on the treatment group to which each subject has been allocated. When the safety set (SS) and the pharmacokinetic analysis set (PKS) are used as analysis sets, analyses will be performed based on the treatment group in which each subject has been actually treated.

- FAS: Population of subjects, excluding the following subjects: subjects with GCP violations, untreated subjects, discontinued subjects before entry to the treatment period, some of the ineligible subjects, and subjects with no available mean NRS score at baseline (Week 0)
- PPS: Population of subjects, excluding the following subjects from the FAS: ineligible subjects, discontinued subjects, deviators, and subjects with broken emergency key codes, as the subjects to be excluded from the PPS

Statistical Analysis Plan	Protocol No. MR13A9-4
	Version: 1.0

- SS: Population of subjects, excluding the following subjects: subjects with GCP violations, untreated subjects, and discontinued subjects before entry to the treatment period
- PKS: Population of subjects, excluding the following subjects from the SS: subjects with no available plasma drug concentration data

Correspondence of the analysis items and the analysis sets is shown in Table 4-1.

Table 4-1 Analysis Items and Analysis Sets

Endpoints	Analysis items	Analysis sets
Demographic and other baseline	Subject demographics	FAS, PPS, SS, PKS
characteristics	Other	SS
Treatment compliance	All items	FAS, SS
Efficacy	Primary variable (primary analysis)	FAS (primary analysis set), PPS
	Other	FAS
Pharmacokinetics	All items	PKS
Safety	All items	SS

5. Analysis Groups

- MR13A9 0.25 μg/kg group: Subjects allocated to or treated with MR13A9 0.25 μg/kg
- MR13A9 0.5 μg/kg group: Subjects allocated to or treated with MR13A9 0.5 μg/kg

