10.1.2 Other assessment variables

10.1.2.1 Change from baseline in the mean NRS score

Summary statistics will be presented. A one-sample t-test will be used for comparisons within each group. A two-sample t-test will be used for comparisons between the placebo group and each of the MR13A9 0.25, 0.5, and $1.0 \mu g/kg$ groups.

Assessment time points: Weeks 1, 2, 3, 4, 5, 6, 7, and 8, Follow-up Weeks 1 and 2

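### PGIC and the follow-up NRS and Shiratori comparisons have only unadjusted tests; if the allocation factors are prognostic these are mildly conservative and lose a little power

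*SAP*

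**What the plan says.** Protocol 7.5.4.4 assigns subjects "by a dynamic allocation method using 2 stratification factors": prior nalfurafine treatment, and specific signs or symptoms in the screening period. The primary MMRM (SAP 10.1.1.1.1) has both factors and baseline mean NRS as covariates and uses Weeks 1 to 8. SAP section 2 adds a similar MMRM for Shiratori, Skindex-16 and 5-D, each with its own baseline.

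Two sets of comparisons fall outside that scheme.

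- **PGIC (SAP 10.2.4; Protocol 13.5.3).** The only test is this: "A two-sample Wilcoxon test will be used for comparisons between the placebo group and each of the" dose groups, once, at the final treatment-period assessment. PGIC is the one listed secondary endpoint with no adjusted analysis.
- **NRS and Shiratori change in follow-up.** SAP 10.1.2.1 states: "A two-sample t-test will be used for comparisons between the placebo group and each of the" dose groups, at Weeks 1-8 and both follow-up weeks. SAP 10.2.1.1 limits the Shiratori model to Weeks 1-8. Its second list, for the other analyses, reads "Others) Weeks 1, 2, 3, 4, 5, 6, 7, and 8, Follow-up Weeks 1 and 2". At the follow-up weeks the t-test is therefore the only between-group comparison of either change score.

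NRS responder rates (SAP 10.1.2.3) are in the same position: Fisher's exact test only, in treatment and in follow-up.

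**The concern.** When allocation forces a prognostic factor into balance, chance imbalance in that factor no longer adds to the variance of the treatment difference. A test that ignores the factor still counts the factor's variance as noise. It overstates the null standard error, rejects less often than its nominal 5%, and gives up power. The SAP accepts this logic for Weeks 1-8 but does not carry it to PGIC or follow-up.

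Baseline score is a separate matter. It is not an allocation factor, so omitting it leaves the error rate at its nominal level. It costs only the precision that a correlated covariate would have bought.

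At stake is some precision in the one patient-rated global measure, and in the only formal look at between-group differences after the drug is stopped.

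**Working it through.** **Inputs from the documents.** 60 per group, allocation 1:1:1:1, two-sided 5%. For Week 8 NRS change, the mean difference from placebo "was assumed to be -0.6, -1.3, and -1.3, respectively, with a common standard deviation of 2.5" (Protocol 7.6.2). No power is stated for PGIC or follow-up.

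**Assumptions (not in the documents).** The share R2 of outcome variance explained by the two factors; their prevalences; the baseline-change correlation r; a 1-point follow-up difference; the Week 8 SD of 2.5 carried into follow-up; no dropout.

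**1. The plan's own figure.** For contrast (3, 1, -2, -2) the signal is 1(-0.6) + (-2)(-1.3) + (-2)(-1.3) = 4.6, and the sum of squared coefficients is 18. Noncentrality = 4.6 / (2.5 x sqrt(18/60)) = 3.36. With 236 df, power is 91.7%, matching the protocol, where the contrast "produced a statistical power of 91.7"%. The pairwise comparison at 1.3 has noncentrality 1.3 / (2.5 x sqrt(2/60)) = 2.848 and power 80.6% (t) to 81.3% (normal), consistent with the stated figure of more than 80%.

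**2. Error rate and power when balanced factors are ignored.** With the factors balanced, the true standard error is the unadjusted one times sqrt(1 - R2). Normal approximation, d = 2.848:

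- size of unadjusted test = 2 x [1 - Phi(1.96 / sqrt(1 - R2))]
- power unadjusted = Phi((d - 1.96) / sqrt(1 - R2))
- power adjusted = Phi(d / sqrt(1 - R2) - 1.96)

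| R2 | Size, unadjusted | Power, unadjusted | Power, adjusted | Points lost |
|---|---|---|---|---|
| 0 | 5.0% | 81.3% | 81.3% | 0 |
| 0.05 | 4.4% | 81.9% | 83.2% | 1.3 |
| 0.10 | 3.9% | 82.5% | 85.1% | 2.6 |
| 0.20 | 2.8% | 84.0% | 89.0% | 5.0 |

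**3. Wilcoxon on a 7-level outcome.** In 4,000 simulated trials per setting, with 240 subjects and minimisation on two binary factors (assignment probability 0.8, assumed), the unadjusted Wilcoxon test had size 4.8%, 4.3%, 4.2% and 3.2% at R2 0, 0.05, 0.10 and 0.20. These sizes carry a simulation error of about 0.3 points.

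**4. Wilcoxon against van Elteren.** 6,000 two-arm comparisons per scenario, 60 per arm, exact balance, factor prevalences 40% and 30%. A factor shifting the latent score by s residual SDs adds variance s^2 x p(1 - p).

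- Shifts of 0.5 and 0.5: 0.25 x 0.24 + 0.25 x 0.21 = 0.1125, so R2 = 0.1125/1.1125 = 0.10. Size 4.2% unstratified v 5.3% stratified; power 70% v 73%.
- Shifts of 0.8 and 0.6: 0.64 x 0.24 + 0.36 x 0.21 = 0.2292, so R2 = 0.2292/1.2292 = 0.19. Size 3.2% v 5.1%; power 66% v 72%.
- No factor effect: the two tests agree at 73%.

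**5. Baseline as a covariate.** With baseline explaining R2 = 0.20 and not used in allocation, simulated size stayed at 5.0% for both the t-test and the Wilcoxon test. Only power moved: 79.8% for the t-test v 87.5% adjusted. For follow-up, noncentrality = 1 / (2.5 x sqrt(2/60)) = 2.19, giving 58% power on 118 df. ANCOVA multiplies the variance by 1 - r^2:

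- r = 0.3: 2.19 / sqrt(0.91) = 2.30, power about 62%
- r = 0.5: 2.19 / sqrt(0.75) = 2.53, power about 71%

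**The case against.** The case for leaving the plan alone is fair in several respects.

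- A plain Wilcoxon test on one ordinal outcome is valid and was prespecified in the protocol. Preferring a stratified version is a matter of efficiency. This stands.
- SAP 6.5 treats everything other than Week 8 NRS change as reference. No claim or sample size depends on PGIC or follow-up, and the primary analysis is adjusted. This stands, and it caps the importance of the point.
- The documents say nothing about how prognostic the factors are. With weak factors almost nothing is lost. This stands, so the loss must be stated conditionally.

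A reader might also infer that omitting baseline makes the p-values conservative. The documents do not support that: Protocol 7.5.4.4 does not balance on baseline score, so its omission leaves the error rate nominal. Nor do the follow-up tests ignore baseline altogether. Their outcome is change from baseline, so baseline is subtracted but not used as a covariate. PGIC has no baseline of its own, since subjects rate change against the screening period (Protocol 9.4.4).

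What the objections do not answer is the inconsistency: the factors and baseline scores are already collected, and the SAP already adjusts for them at Weeks 1-8.

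**Conclusion.** The gap is real and small. PGIC, and NRS and Shiratori change at Follow-up Weeks 1 and 2, have no adjusted between-group comparison. If the two allocation factors are prognostic, their tests are somewhat conservative and lose power: nothing at R2 0, about 1 point at 0.05, and about 3 to 6 points at 0.10-0.20, with a Wilcoxon error rate of about 4.2% to 3.2%. Separately, a baseline-change correlation of 0.3-0.5 would raise follow-up power for a 1-point difference from 58% to about 62-71%.

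Every one of these sizes rests on assumed prognostic strength, and the follow-up figures also on an assumed difference and an SD borrowed from Week 8. It would be going too far to read this as a threat to the trial's conclusions: the error is towards caution, no false-positive rate is inflated, and the primary analysis is unaffected.

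**What to change.** - **PGIC:** make a van Elteren test, stratified by the four combinations of the two allocation factors, the main comparison of each dose with placebo.
- **NRS and Shiratori change at Follow-up Weeks 1 and 2:** use ANCOVA at each week, with the relevant baseline score and the two allocation factors as covariates.
- **Keep** the protocol's Wilcoxon test and t-tests as supplementary, and list the change in SAP section 2.
- **Optionally,** give the NRS responder rates in SAP 10.1.2.3 a Cochran-Mantel-Haenszel test over the same strata, next to Fisher's exact test.

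The cost is some SAP wording, standard procedures and a few extra outputs. No new data are needed, and the analyses stay reference analyses. The change should be written in before database lock.

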10.3 Efficacy Subgroups

Among "10.1.1.1 Analysis of the primary variable," the same analysis as "10.1.1.1.1 Primary analysis" will be performed for each subgroup shown in Table 10.3-1. However, the subgroup variables will be excluded from the model covariates. Assessment of the dose-response relationship using contrasts will not be conducted.

Table 10.3-1 Subgroups

Item	Class
Prior treatment with nalfurafine hydrochloride	No, Yes
Specific signs or symptoms to be confirmed in the screening period	No, Yes

Statistical Analysis Plan	Protocol No. MR13A9-4
Statistical Analysis Plan	Version: 1.0

11. Pharmacokinetics

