10.1.1.1 Analysis of the primary variable

10.1.1.1.1 Primary analysis

The primary analysis will be performed using a mixed-effects model for repeated measures (MMRM) with the change from baseline in the mean NRS score at each time point as an objective variable; treatment group, time point, and treatment group-by-time point interaction as fixed effects; baseline mean NRS score and dynamic allocation factors, including the presence of prior treatment with nalfurafine hydrochloride, and the presence of specific signs or symptoms to be confirmed in the screening period, as covariates; and subject as a random effect.

The analysis will include all available data obtained at each time point between Week 1 and Week 8 of the treatment period. Estimation will be performed using a restricted maximum likelihood method. An unstructured covariance structure will be used to estimate error variance. If the unstructured covariance structure fails to provide convergence, the structure that minimizes Akaike's Information Criterion (AIC), among the Toeplitz, first-order autoregressive, and compound symmetry structures will be used. The degree of freedom will be adjusted with the Kenward-Roger method.

For the primary variable and the change from baseline in the mean NRS score at Week 2 of the treatment period, contrasts will be used to determine the dose-response relationship for the placebo group and the MR13A9 0.25, 0.5, and 1.0 μ g/kg groups. Contrast patterns (placebo, 0.25, 0.5, 1.0 μ g/kg) to be used will include (3, 1, -1, -3), (2, 2, -1, -3), (1, 1, 1, -1, -1), (3, -1, -1, -1), and (3, 1, -2, -2).

The number of subjects, adjusted mean of the change, standard error, and two-sided 95% confidence interval in each group at each time point will be presented, and the adjusted mean and standard error will be presented in graphs. The adjusted mean between-group difference in the change at each time point for the placebo group and the MR13A9 0.25, 0.5, and $1.0~\mu g/kg$ groups and its two-sided 95% confidence interval as well as the p-value will be

Protocol No. MR13A9-4
Version: 1.0

presented. P-values will be presented for each contrast pattern used to examine the dose-response relationship.

Assessment time points: Weeks 1, 2, 3, 4, 5, 6, 7, and 8

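### SAP 10.3 gives p-values within each efficacy subgroup level but no estimate or test of the difference between levels, so chance discordance can be misread as a difference in effect

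*SAP*

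**What the plan says.** SAP 10.3 states that the primary analysis "will be performed for each subgroup shown in Table 10.3-1. However, the subgroup variables will be excluded from the model covariates", and it drops the dose-response contrasts. Table 10.3-1 lists two yes/no factors: prior nalfurafine, and specific signs or symptoms in screening. These are the two dynamic-allocation factors in Protocol 7.5.4.4.

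What carries over from SAP 10.1.1.1.1 is, for each level, the adjusted difference from placebo for each dose at each of eight weeks, with its 95% CI and p-value. SAP section 3 sets the general rule: "All statistical tests will be performed using a two-sided significance level of 5" per cent. The model terms are treatment, week, treatment by week and covariates. No treatment-by-subgroup term or test appears in SAP 6.8, 10.1.1.1.1 or 10.3, and Protocol 13.5 describes no efficacy subgroup analysis.

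Removing the subgroup variable from the covariates is not itself a fault, since it is constant within its own stratum.

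**The concern.** The question a subgroup analysis raises is whether the effect differs between levels. The plan tests a different question twice: whether each level, alone, differs from placebo. Each stratum has less power than the whole trial, so one can reach significance and the other miss it when the true effects are the same.

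The comparison is a natural one to make here. Protocol 1.2 and 1.3 describe both nalfurafine and MR13A9 as KOR agonists, and prior nalfurafine is one of two entry routes in Protocol 4.1.1. That readers will compare its two levels is my inference; the documents do not state it. What is at stake is the reading of the subgroup tables only.

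**Working it through.** **Inputs.** From Protocol 7.6.2: the Week 8 difference from placebo "was assumed to be -0.6, -1.3, and -1.3, respectively, with a common standard deviation of 2.5" for 0.25, 0.5 and 1.0 μg/kg, "with a two-sided significance level of 5% and a sample size of 60 subjects per group". Stratum sizes are not given, so I assume splits of each group of 60 from 30/30 to 48/12, the same in every arm. Week 8 only; missing data and any gain from covariates or repeated measures are ignored.

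**Step 1: reproduce the plan's figures.** For "a contrast pattern of 3, 1, -2, -2":
- Contrast value: 1×(−0.6) − 2×(−1.3) − 2×(−1.3) = 4.6.
- SE = 2.5 × √[(9+1+4+4)/60] = 1.369, so the noncentrality is 4.6/1.369 = 3.36 on 236 df.
- Power by noncentral t is 91.7%, as the protocol states ("produced a statistical power of 91.7" per cent).
- For one higher dose against placebo: SE = 2.5 × √(2/60) = 0.456, noncentrality 2.85, power about 81%. This agrees with the protocol's claim of more than 80%.

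**Step 2: power within a stratum, same true effect in both.** With n per arm in the stratum, SE = 2.5 × √(2/n), noncentrality = effect/SE, df = 4n − 4. For −1.3:
- n = 30: SE 0.645, noncentrality 2.01
- n = 12: SE 1.021, noncentrality 1.27
- n = 48: SE 0.510, noncentrality 2.55

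**Step 3: chance that exactly one stratum is significant.** The strata contain different patients, so P = p1(1 − p2) + p2(1 − p1).

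| Split per arm | Power, −1.3 | Exactly one, −1.3 | Power, −0.6 | Exactly one, −0.6 |
|---|---|---|---|---|
| 30/30 | 51.5% / 51.5% | 50.0% | 15.0% / 15.0% | 25.4% |
| 42/18 | 65.9% / 33.7% | 55.2% | 19.3% / 10.6% | 25.8% |
| 48/12 | 71.7% / 23.8% | 61.4% | 21.5% / 8.3% | 26.2% |

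Example, 48/12: 0.717 × 0.762 + 0.238 × 0.283 = 0.614. At 30/30, both strata are significant in 26.5% of such trials and neither in 23.5%.

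**Step 4: what a direct comparison would give.** The difference between strata in one dose effect has SE = 2.5 × √(2/n1 + 2/n2).

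| Split per arm | SE | 95% CI half-width | Power for a 1.3-point difference | Difference detectable with 80% power |
|---|---|---|---|---|
| 30/30 | 0.91 | 1.8 | 30% | 2.6 |
| 48/12 | 1.14 | 2.2 | 21% | 3.2 |

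Power here is by normal approximation for one dose, not for a joint test over doses. With equal true effects, a 5% test of one such difference flags falsely in 5% of trials. One joint test per factor gives 1 − 0.95² = 9.75% for at least one false flag over the two factors, if independent. Six separate dose-by-factor tests would give 1 − 0.95⁶ = 26.5%.

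**The case against.** **The misreading is not planned.** SAP 10.3 makes no subgroup claim and sets no rule for comparing significance. SAP 6.5.2 and 6.5.3 handle everything outside the primary variable as reference. This stands and limits the weight of the point. But those sections explain why multiplicity is not adjusted; they do not say how strata may be compared, and the p-values are still produced.

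**The information is nearly there.** Each stratum reports estimates and CIs from separate patients, so a reader could subtract them and approximate a CI for the difference. That is true, and a good reason not to overrate the problem. Still, the relevant quantity is left for the reader to derive.

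**An interaction test has little power.** Step 4 confirms it. This argues for showing the difference with its interval, and against reading a non-significant result as equality.

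**Stronger readings that the documents do not support:**
- A reader might infer that discordance is bound to appear. For one higher dose it is roughly an even chance or somewhat more, and about one in four for 0.25 μg/kg.
- A reader might infer that the two strata will be fitted with different covariance structures. SAP 10.1.1.1.1 says "An unstructured covariance structure will be used to estimate error variance", which for eight weeks means 8 × 9/2 = 36 parameters, with a fallback if the fit does not converge. But the fallback is prespecified. Even at 12 per arm a stratum has 48 subjects, with one matrix pooled over arms. Nothing shows that convergence would fail.
- A reader might infer that these results will choose the next trial's population. Neither document says so; the stated objective is dose-response.

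**Conclusion.** The point holds as a gap in the subgroup analysis. The plan yields dose-versus-placebo results within each level and nothing on the difference between levels. With identical true effects, exactly one stratum would be significant in about 50% to 61% of trials for each of 0.5 and 1.0 μg/kg, and in 25–26% for 0.25 μg/kg. The output can therefore be misread as a difference in effect.

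These figures rest on the protocol's planning effects and SD, on assumed splits, and on the Week 8 simplification above; missing data would lower stratum power, and covariate adjustment would raise it. The primary analysis and its dose-response contrasts are unaffected. The subgroups are few, prespecified and reported with intervals, so the consequence is confined to exploratory interpretation.

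**What to change.** For each factor, add to SAP 10.3 one MMRM on the FAS with treatment, week, subgroup and all their interactions, plus the other covariates. At Week 8 report:
- each dose-minus-placebo difference by stratum, with 95% CI;
- the difference between strata for each dose, with 95% CI;
- one joint 3-df treatment-by-subgroup p-value per factor, labelled exploratory.

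State that within-stratum p-values are not to be compared between strata, and that a non-significant interaction is not evidence of equal effects. Whether to keep the within-stratum p-values, and whether the pooled model uses one covariance matrix or one per stratum, is a matter of preference; the SAP should settle it in advance.

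The cost is a short SAP paragraph and some code; no new data are needed. The downside is an imprecise interaction estimate, which the interval will show openly.
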